8.3.8 Potential Drug-Induced Liver Injury

Wherever possible, timely confirmation of initial liver-related laboratory abnormalities should occur prior to the reporting of a potential DILI event. All occurrences of potential DILIs, meeting the defined criteria, must be reported as SAEs (see [APPENDIX 3](#) for reporting details).

Potential DILI is defined by presence of all of the following characteristics:

- ALT or AST elevation $> 3 \times$ ULN
- total bilirubin $> 2 \times$ ULN, without initial findings of cholestasis (elevated serum alkaline phosphatase)
- no other immediately apparent possible causes of AST or ALT elevation and hyperbilirubinemia, including, but not limited to, viral hepatitis, preexisting chronic or acute liver disease, or the administration of other drug(s) known to be hepatotoxic

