11.8.4 Laboratory Data

Laboratory parameters will be summarized using both the International System (SI) of Units and conventional system of Units, unless otherwise specified. Summaries will be provided separately by different panels including hematology, general chemistry, chemistry - hepatobiliary, chemistry - renal function tests, chemistry - coagulation, and urinalysis. Only lab assessments with collection date up to last dose day +30 days post last dose day or up to first dose day of study IM011-074 for roll over subjects will be summarized. Data will be summarized by analysis visit, as applicable. The following summaries will be provided for each parameter:

- Absolute and change from baseline values
- Laboratory abnormalities (as determined by Controlled Terminology Criteria for Adverse Events [CTCAE v5.0] grading) presented as the worst postbaseline toxicity group

Sponsor: Bristol-Myers Squibb
Protocol no: IM011021

- Shifts from baseline to maximum postbaseline value
 - Potential drug induced liver injury (DILI) is defined as a subject who meets the following criteria on the same assessment date:
 - 1) ALT or AST elevation >3 times ULN
AND
 - 2) Total bilirubin >2 times ULN
AND
 - Normal serum alkaline phosphatase (No initial findings of cholestasis)
 - ALT or AST elevation >5 times ULN
- All abnormalities in laboratory data will be provided in listings.

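### The SAP counts potential drug-induced liver injury only when all laboratory criteria fall on one date, a condition the protocol definition does not state, so some non-concurrent cases would be missing from the summary

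*SAP*

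**What the plan says.** **SAP 11.8.4 (Laboratory Data).** The rule reads: "Potential drug induced liver injury (DILI) is defined as a subject who meets the following criteria on the same assessment date". The criteria, joined by AND, are "ALT or AST elevation >3 times ULN", "Total bilirubin >2 times ULN" and "Normal serum alkaline phosphatase (No initial findings of cholestasis". The section appears to list ALT/AST above 5 times ULN as a separate category. It summarises samples up to 30 days after the last dose (or up to the first extension-study dose for roll-over subjects) and lists all laboratory abnormalities.

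**Protocol 8.3.8 (Potential Drug-Induced Liver Injury).** "Potential DILI is defined by presence of all of the following characteristics". The ALT/AST and bilirubin thresholds match the SAP's. The bilirubin criterion is qualified by "without initial findings of cholestasis (elevated serum alkaline phosphatase", and a third characteristic requires that no other cause be immediately apparent. There is no same-date condition and no time window. On reporting: "All occurrences of potential DILIs, meeting the defined criteria, must be reported as SAEs".

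**SAP change lists.** Section 5.5 records that the alternative-cause condition was removed from 11.8.4. Section 5.4.2 labels the SAP's departures from the protocol's SRI definition as corrections or clarifications. No visible entry mentions or justifies the same-date condition. Some item numbers are missing from the public copy.

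**The concern.** The SAP applies a different rule from the protocol under the same name. Transaminases and bilirubin need not cross their thresholds at the same draw. If ALT/AST is already falling when bilirubin rises, no single date may satisfy every criterion. The SAP also tests ALP on the qualifying date, although both documents speak of initial findings of cholestasis.

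This is the only dedicated liver-injury summary in the visible SAP. The adverse events of interest in SAP 11.8.2 include no hepatic category, and SAEs in 11.8.3 are tabulated by body system and preferred term. The study report could show no potential DILI in the laboratory table beside a potential-DILI SAE, with no stated rule for reconciling them.

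**Working it through.** The documents give no figure to reproduce. The check sets the two definitions side by side and then applies each to assumed laboratory sequences.

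**Definitions**

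| Element | Protocol 8.3.8 | SAP 11.8.4 |
|---|---|---|
| ALT or AST | >3 × ULN | >3 × ULN |
| Total bilirubin | >2 × ULN | >2 × ULN |
| ALP | No initial cholestasis | Normal on the qualifying date |
| Other apparent cause | Must be absent | Not considered |
| Timing | Not stated | Same assessment date |

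**Sampling interval.** The schedules of activities place chemistry on Days 1, 15, 29 and 57, then every 28 days to Day 337. From Day 29 the target gap is 28 days. With ±3 days at each visit, the gap can run from 28 − 6 = 22 to 28 + 6 = 34 days. ALT, AST, bilirubin and ALP belong to one chemistry panel (protocol 8.5.3), so they are normally measured together.

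**Assumed sequences.** These values are illustrations, not taken from the documents. Units are multiples of ULN, AST is assumed no higher than ALT, and no other cause is present except in (e).

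| | Day 57 | Day 85 | Protocol 8.3.8 | SAP 11.8.4 |
|---|---|---|---|---|
| (a) | ALT 5, bilirubin 1, ALP normal | ALT 2, bilirubin 2.5, ALP normal | Could be judged potential DILI; timing not addressed | Not counted |
| (b) | ALT 5, bilirubin 1, ALP normal | ALT 3.5, bilirubin 2.5, ALP normal | Met | Counted on Day 85 |
| (c) | ALT 5, bilirubin 2.5, ALP normal | any | Met | Counted on Day 57 |
| (d) | ALT 5, bilirubin 1, ALP normal | ALT 3.5, bilirubin 2.5, ALP raised | Could be judged potential DILI if initial means at onset | Not counted |
| (e) | As (c), with viral hepatitis apparent | any | Not met | Counted |

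Sequences (a) and (d) are missing from the SAP count. Sequence (b) shows that a later bilirubin rise is not missed merely because it is later. Sequence (e) shows the SAP count exceeding the protocol count.

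**Scale.** With about 90 subjects per arm (SAP 5.1), one subject is 1/90 = 1.1% of an arm.

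**The case against.** The strongest reply is that the protocol is silent on timing. Requiring all characteristics to be present can be read as requiring them together, in which case the SAP only settles an open point. This stands in part: a reader might infer that the SAP contradicts the protocol, or that every non-concurrent case must be reported as an SAE, and the text supports neither. It does support saying that the SAP adds an unexplained restriction.

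A reader might also infer that any bilirubin rise first seen at a later or unscheduled draw is lost. That is not so. The SAP counts a subject on any single date that meets all criteria, and its wording refers to assessment dates, so it does not exclude unscheduled draws.

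Other planned outputs would show much of the information: SAE tables and listings, worst CTCAE grade, shifts to the maximum value, the category above 5 times ULN, and listings of abnormalities and of all data (SAP 11.0). This also stands, and it means that no new listing is essential. However, the summaries by parameter do not combine the ALT/AST and bilirubin series, and the SAE route depends on investigator judgement.

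Finally, pairing elevations over the whole treatment and safety period would admit unrelated pairs. Protocol 5.2 allows entry with bilirubin above its limit when this is related to SLE or to documented Gilbert's syndrome, and the SAP no longer screens for other causes. This is a sound objection to an open-ended window, not to a bounded one.

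**Conclusion.** The point holds in a limited form. A subject is missing from the SAP summary when ALT/AST is at or below 3 times ULN, or ALP is not normal, on every date on which bilirubin exceeds 2 times ULN. Such a case could be judged potential DILI under protocol 8.3.8. This rests on reading the protocol's silence as leaving timing open.

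It would be wrong to conclude that the SAP always undercounts, because dropping the alternative-cause condition broadens its rule in another respect. The net direction is unknown. Nor would it be right to say that liver cases disappear from the report, given the SAE and listing routes.

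The consequence is confined to a descriptive safety summary. Treatment stopping and SAE reporting follow protocol 7.1 and 8.3.8 and do not depend on this table. The change is still worth making, because a single case alters a sparse row and the correction uses data already collected.

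**What to change.** In SAP 11.8.4:

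1. Keep the same-date row.
2. Add a row for bilirubin above 2 times ULN on, or within a prespecified number of days after, an ALT/AST elevation above 3 times ULN. Stay inside the existing limit of 30 days after last dose (or first extension dose), and assess ALP at the onset of the ALT/AST elevation.
3. Justify the chosen interval. The documents give no value. To reach the next scheduled draw from Day 29 onward at the widest permitted spacing, it would need to cover 34 days; a shorter interval would rely more on unscheduled or early draws.
4. Label both rows as laboratory screens that do not consider other causes.
5. Reconcile flagged subjects with potential-DILI SAEs reported under protocol 8.3.8, and explain differences in either direction.

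The cost is one table row and a short reconciliation. Some subjects without DILI may be flagged and need review. No new data are needed, and no efficacy analysis or clinical rule changes.

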11.8.5 Vital Signs

Vital signs including body temperature, respiratory rate, systolic blood pressure (SBP) and diastolic blood pressure (DBP), and heart rate will be listed. Absolute lab values, change from baseline values will be reported with summary statistics by treatment group and analysis visit.

The summaries of marked abnormalities at any timepoint postbaseline will also be tabulated for definitions provided as below.

- Absolute and change from baseline values
- Marked abnormalities defined by the below categories:
 - Heart rate:
 - Value > 100 and change from baseline > 30
 - Value < 55 and change from baseline < -15
 - Systolic blood pressure:
 - Value > 140 and change from baseline > 20
 - Value < 90 and change from baseline < -20
 - Diastolic blood pressure:
 - Value > 90 and change from baseline > 10
 - Value < 55 and change from baseline < -10

11.8.6 ECG

Summary statistics will be presented for ECG observed values, change from baseline values for all ECG parameters by treatment group and analysis visit.

The summaries of marked abnormalities at any timepoint post-baseline will also be tabulated for definitions provided as below.

- Absolute and change from baseline values
- Marked abnormalities defined by the below categories:
 - QT interval corrected using Fridericia's formula (QTcF):
 - 450 -< 480 msec
 - 480 -< 500 msec

Sponsor: Bristol-Myers Squibb
Protocol no: IM011021

- ≥ 500 msec
 - $30 < \text{change from baseline} \leq 60$ msec
 - Change from baseline > 60 msec
 - Males: < 450 msec, ≥ 450 msec
 - Females: < 470 msec, ≥ 470 msec
- PR interval ≥ 200 msec
 - QRS interval ≥ 200 msec

In cases where QTcF is missing, then QTcF will be derived using the following definition: $QTcF = QT / (RR^{1/3})$, where RR (seconds) = $60 / \text{HR}$. In case where both QTcF and QT are missing, then QTcF will be derived using the following definition: $QTcF = QTcB / (RR^{1/6})$, where RR (seconds) = $60 / \text{HR}$.

Additionally, all ECG data will be provided in a listing.

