- Proportion of subjects with a Cutaneous Lupus Erythematosus Disease Area and Severity Index (CLASI) activity score \geq 10 at baseline who achieve a CLASI response, defined as a decrease of \geq 50% from baseline CLASI activity score at Week 48
- Change from baseline in the 40-joint count for tender, swollen, and tender + swollen joints at Week 48

Objective

Endpoint

Safety

- To assess the safety and tolerability of BMS-986165
- Number and proportion of subjects experiencing serious adverse events (SAEs); adverse events (AEs); and abnormalities in laboratory testing, vital signs, and electrocardiograms (ECGs)

Overall Design:

This is a randomized, placebo-controlled, double-blind, multicenter study to evaluate the efficacy and safety of BMS-986165 in subjects with SLE. The study includes a screening period (SP) of up to 4 weeks (28 days); a 48-week (336-day) blinded treatment period (TP); and a 28-day follow-up period (FP), for subjects who do not continue into the long-term extension (LTE) study (IM011074). The total duration will be approximately 56 weeks (392 days). Other details of study design are as follows:

- Randomization will be performed after completion of the SP, on Day 1 of the TP.
- Randomization in a 1:1:1:1 ratio will be performed using interactive response technology (IRT) and will be stratified by screening corticosteroid (CS) dose (≥ 10 mg/day or < 10 mg/day), screening SLEDAI-2K score (≥ 10 or < 10), and geographic region.
- The blind will be maintained during the TP by the use of matched capsules (placebo and 3 mg BMS-986165) provided in blister cards that are identical in appearance while providing the appropriate randomized dose.
- Clinical, laboratory, and photographic evidence of disease activity will be reviewed by blinded external reviewers.
- Safety data will be reviewed by the Data Monitoring Committee.
- The primary analysis of Week 32 efficacy assessments will be performed after all subjects have completed 48 weeks of double-blind treatment (or discontinued from the study).

Number of Subjects:

Approximately 360 subjects will be randomized to receive oral treatment with BMS-986165 12 mg once daily (QD), 6 mg twice daily (BID), 3 mg BID, or placebo BID.

Treatment Arms and Duration:

Study treatment: Subjects in all treatment groups will take oral doses of the investigational product (IP) for 48 weeks during the TP as follows: BMS-986165 12 mg QD, 6 mg BID, 3 mg BID, or placebo BID.

[figure not shown]

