8.3.9 Other Safety Considerations

Any significant worsening noted during interim or final physical examinations, ECG, X-ray filming, any other potential safety assessment required or not required by protocol should also be recorded as a nonserious or serious AE, as appropriate, and reported accordingly.

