9.3.2 Safety Analyses

Safety analyses will be performed using the As-treated population. The primary safety endpoint is a secondary endpoint of the study. For analysis, all recorded AEs will be listed and tabulated by system organ class, preferred term, and treatment. Vital signs and clinical laboratory test results will be listed and summarized by treatment. ECG readings will be evaluated by the investigator and abnormalities, if present, will be summarized and listed.

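### The QRS row of the marked ECG abnormality table uses 200 msec, the same limit as PR, with no explanation, so it is unlikely to give a useful count of QRS widening by arm

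*SAP*

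**What the plan says.** The Protocol (Synopsis and Table 4) makes the safety endpoint the number and proportion of subjects with adverse events and with "abnormalities in laboratory testing, vital signs, and electrocardiograms (ECGs").

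SAP 11.8.6 turns the ECG part of this into three outputs:

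- **Continuous summaries:** "Summary statistics will be presented for ECG observed values, change from baseline values for all ECG parameters by treatment group and analysis visit". SAP 11.0 includes the quartiles, minimum and maximum among the summary statistics.
- **A categorical table:** "The summaries of marked abnormalities at any timepoint post-baseline will also be tabulated for definitions provided as below". QTcF gets three absolute tiers, two change-from-baseline tiers and sex-specific limits. The other two intervals get one line each: "PR interval ≥ 200 msec" and "QRS interval ≥ 200 msec".
- **A listing:** "Additionally, all ECG data will be provided in a listing".

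The Protocol adds two routes that do not depend on the cut-off. Section 9.3.2 states that "ECG readings will be evaluated by the investigator and abnormalities, if present, will be summarized and listed". Section 8.3.9 has significant worsening on ECG recorded as an adverse event.

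**The concern.** PR and QRS are different conduction intervals, yet they share one limit, and the SAP does not say why. Neither document gives any other QRS limit. The QRS line also has less structure than its neighbours. QTcF has graded values and graded changes, and every heart-rate and blood-pressure criterion in SAP 11.8.5 pairs a value with a change. If 200 msec is too high for QRS, no other criterion in the table makes up for it.

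What is at stake is the part of the safety endpoint expressed as a proportion. The marked-abnormality table is the only categorical ECG output that SAP 11.8.6 defines. If its QRS row is nearly certain to be empty in every arm, the row carries little information on whether the drug widens QRS, and a zero in it should not be read as evidence of no effect.

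**Working it through.** The 200 msec limit is a definition, so there is no calculated figure to reproduce. The check is how often a QRS value would reach it.

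**Inputs from the documents.** The QRS limit is 200 msec (SAP 11.8.6). About 360 subjects are planned, about 90 per arm (SAP 5.1). Five post-baseline ECGs are scheduled, at Weeks 4, 8, 12, 32 and 48 (Protocol Tables 2 and 3).

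**Inputs assumed.** The documents give no QRS distribution. I take a normal distribution with mean 85 to 105 msec and SD 10 to 20 msec. For subjects whose QRS is already wide, I take mean 135 to 160 msec and SD 15 to 20 msec. For comparison I use a lower limit of 120 msec, a conventional ECG limit that is also not in the documents.

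**Formula.** P(QRS ≥ L) = 1 − Φ((L − mean)/SD). Expected subjects for one reading each = 360 × P.

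| Assumed mean, SD (msec) | SDs to 200 | P(≥ 200) | Expected of 360 | SDs to 120 | P(≥ 120) | Expected of 360 |
|---|---|---|---|---|---|---|
| 85, 10 | 11.5 | negligible | negligible | 3.5 | 0.0002 | 0.1 |
| 95, 15 | 7.0 | 1.3 × 10⁻¹² | 4.6 × 10⁻¹⁰ | 1.67 | 0.048 | 17.2 |
| 105, 20 | 4.75 | 1.0 × 10⁻⁶ | 0.0004 | 0.75 | 0.227 | 81.6 |

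The table counts a value at any post-baseline visit. Five readings raise the least favourable figure to at most 5 × 0.0004 = 0.002 expected subjects.

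**Subjects with an already wide QRS.** P(≥ 200) per reading runs from 0.00001 (mean 135, SD 15) through 0.003 (mean 145, SD 20) to 0.023 (mean 160, SD 20). At the top of that range, five readings give at most 5 × 0.02275 = 0.114 per subject. An arm would then need about 1/0.114 ≈ 9 such subjects to expect one entry in the row.

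**Can the continuous summaries stand in?** Suppose one subject in an arm of 90 goes from 95 to 160 msec. The arm mean moves by 65/90 = 0.7 msec, which would not be noticed. The observed maximum at that visit would be at least 160 msec and the maximum change at least 65 msec, so the case itself is visible. The number of subjects affected in each arm is not.

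**The case against.** The strongest reply is that the limit governs one row of one descriptive table and that QRS is reported in several other ways. That is correct. A reader might infer from the 200 msec limit that QRS widening or bundle-branch block would go unreported. The documents do not support that. Observed values and changes are summarised for every ECG parameter with maxima, all ECG data are listed, Protocol 9.3.2 commits to a summary of investigator-judged abnormalities with no numerical cut-off, and Protocol 8.3.9 sends significant worsening to adverse event reporting.

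Three other inferences also go too far:

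- **That the line was copied from PR.** This is possible, but a deliberately high limit for a marked abnormality would look the same. The documents cannot separate the two.
- **That the row must stay empty whatever the drug does.** A large enough effect would fill it. From an assumed 95 msec, a subject would have to widen by 105 msec.
- **That 120 msec is the limit the plan should have used.** Neither document gives that figure or any other normal range for QRS.

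It is also fair to say that PR has no change criterion either, that conduction is not an adverse event of interest (Protocol 8.3.1, SAP 11.8.2), and that clinically significant ECG abnormalities are excluded at entry (Protocol 5.2, criterion 5a).

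Part of the point survives. The investigator summary promised in Protocol 9.3.2 is not specified in SAP 11.8.6. Adverse event capture depends on each investigator judging the change significant. Maxima and listings show cases but do not apply one numerical rule to every subject. None of these routes gives a uniform proportion by arm.

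**Conclusion.** The point holds for the marked-abnormality table. Its QRS criterion equals the PR criterion, is unexplained and has no lower tier or change category. The row is likely to be empty or nearly empty: under the assumed distributions, fewer than 0.001 expected subjects among 360 for one reading each, and at most 2.3% per reading among subjects with an already wide QRS. These sizes rest on normality and on means and SDs that are not in the documents. The conclusion is stable across the ranges shown.

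The point does not extend to ECG reporting as a whole, because the other outputs could show individual cases. Severity is minor. No efficacy analysis, dose comparison or stopping rule depends on this row.

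**What to change.** In SAP 11.8.6, before unblinding:

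1. State whether 200 msec for QRS is intended. If it is, keep it as a top tier and give the reason.
2. Add a lower QRS tier. A limit of 120 msec is offered as an example and should be recorded as the sponsor's choice, since the documents give none.
3. Tabulate by arm the treatment-emergent version: any post-baseline value at or above the lower limit in a subject whose baseline was below it. This stops pre-existing wide QRS from dominating the count.

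The change affects one SAP item and uses ECGs already scheduled, with no new visits or measurements. The cost is more flagged values to review. The number depends on the true distribution: under the assumptions above it runs from 0.1 to about 82 of 360 for a single reading at 120 msec, with about 17 in the middle case. Subjects already at or above the limit at baseline would drop out of the treatment-emergent version.

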5.5 Summary of Changes to Version 3.0 of SAP

No analyses were performed prior to the revision of this SAP.

1. Added clarification for the first dose date in section 7.1
2. Added one additional condition in sections 11.7.1 and 11.7.2.2:
 - a. Subjects takes any medications included in protocol Appendix 7 between first dose date and efficacy assessment visit
3. Deleted one condition in sections 11.7.1 and 11.7.2.2:
 - a. Initiations and/or increases which occur for less than 4 days are permitted
4. Deleted the bar chart in sections 11.7.1, 11.7.2.3 and 11.7.2.4
5. In section 11.7.1, in case the logistic regression model fit is not stable the region stratification factor may be removed from the model. The stratification factors were updated to: CS dose ≥ 10 mg/day Yes or No, SLEDAI-2K score ≥ 10 Yes or No, and Japan.
6. Added clarification for analysis time points in section 11.7.2.5
7. Changed "interferon regulated genes" to "interferon" in section 11.7.4
8. Added "at baseline" for subgroup analyses referring to CS Use, anti-malarial use, and immunosuppressant use in section 11.7.4
10. Added clarification for analysis time points in section 11.7.5
11. Deleted the following condition in section 11.8.4:

Sponsor: Bristol-Myers Squibb
Protocol no: IM011021

- a. No other immediately apparent possible causes of liver function test elevation and hyperbilirubinemia, including, but not limited to, viral hepatitis, preexisting chronic or acute liver disease, or the administration of other drug(s) known to be hepatotoxic.
12. Modified the QTcF calculation in section 11.8.6
13. Updated the pharmacokinetic analyses in section 12.0
14. Updated the biomarker analyses in section 13.0
15. Updated the biomarker listing in [appendix 6](#)

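### The SAP's fallback for deriving QTcF from QTcB divides by RR^(1/6) where it should multiply, so the value is about 19% too high at 100 bpm and 6% too low at 50 bpm.

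*SAP*

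**What the plan says.** SAP section 11.8.6 (ECG) tabulates marked abnormalities in the "QT interval corrected using Fridericia's formula (QTcF"). The absolute bands are 450 to below 480, 480 to below 500, and 500 msec or more. There are two bands for change from baseline, above 30 up to 60 msec and "Change from baseline > 60 msec", and sex-specific cut-offs at 450 msec (males) and 470 msec (females). A subject is counted for an abnormality at any post-baseline time point.

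The section has three tiers for obtaining QTcF:

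1. Use the recorded QTcF.
2. If it is missing, compute QT/RR^(1/3).
3. "In case where both QTcF and QT are missing, then QTcF will be derived using the following definition": "QTcF = QTcB / (RR^{1/6"), that is, QTcB divided by the sixth root of RR.

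Tiers 2 and 3 both set RR, in seconds, to 60/HR. The SAP does not define QTcB.

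The change log for SAP Version 3.0 (section 5.5) records "Modified the QTcF calculation in section 11.8.6". The log for Version 4.0 (section 5.6) lists only a wording change in section 11.5.2, so the formula is current text.

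**The concern.** Tiers 2 and 3 are meant to yield the same quantity from different inputs, so they should agree for any heart rate. As printed they agree only at 60 bpm, where RR = 1.

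The error depends on heart rate and runs both ways. Above 60 bpm the fallback shows prolongation that is not there; below 60 bpm it can hide prolongation that is. It matters most for change from baseline: if one of the two values is recorded and the other comes from the fallback, the whole error appears as a change. Because the tables count any post-baseline occurrence, and each ECG is a single 12-lead reading (Protocol Table 1), one wrong value is enough to misclassify a subject. ECG abnormalities are a named safety endpoint (Protocol Table 4).

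**Working it through.** **Inputs**

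- Fridericia, from SAP 11.8.6: QTcF = QT/RR^(1/3).
- Fallback, from SAP 11.8.6: QTcF = QTcB/RR^(1/6).
- RR = 60/HR seconds, from SAP 11.8.6: 1.2 at 50 bpm, 1.0 at 60, 0.75 at 80, 0.6 at 100 and 0.5 at 120.
- Assumption from outside the SAP: QTcB is the Bazett correction, QTcB = QT/RR^(1/2).

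**Algebra**

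- From Bazett, QT = QTcB × RR^(1/2).
- Put into the SAP's Fridericia formula: QTcF = QTcB × RR^(1/2)/RR^(1/3) = QTcB × RR^(1/2 - 1/3) = QTcB × RR^(1/6).
- The printed fallback gives instead QTcB/RR^(1/6) = QT/RR^(1/2 + 1/6) = QT/RR^(2/3).
- Ratio of printed to correct: RR^(1/3)/RR^(2/3) = RR^(-1/3).

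The exponent 1/6 is exactly 1/2 - 1/3, so the intended conversion is plain; only the operator is wrong.

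**Size for a true QTcF of 400 msec**

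| HR (bpm) | RR (s) | QTcB | SAP fallback | Corrected fallback | Error |
|---|---|---|---|---|---|
| 50 | 1.2 | 388.0 | 376.4 | 400.0 | -5.9% |
| 60 | 1.0 | 400.0 | 400.0 | 400.0 | 0 |
| 75 | 0.8 | 415.2 | 430.9 | 400.0 | +7.7% |
| 80 | 0.75 | 419.6 | 440.3 | 400.0 | +10.1% |
| 100 | 0.6 | 435.5 | 474.3 | 400.0 | +18.6% |
| 120 | 0.5 | 449.0 | 504.0 | 400.0 | +26.0% |

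**Worked records (QT values are illustrative)**

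- HR 100, QT 340: QTcB = 340/0.6^(1/2) = 438.9. Multiplying by 0.6^(1/6) = 0.9184 gives 403.1, which equals 340/0.6^(1/3). Dividing gives 477.9, an error of +75 msec.
- HR 80, QT 370: correct 407.2, printed 448.2, an error of +41 msec.
- HR 50, QT 480: correct 451.7, printed 425.1, an error of -27 msec. The record leaves the 450 to below 480 band.

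**Effect on the 450 msec cut-off.** The printed value reaches 450 when the true value reaches 450 × RR^(1/3):

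- 100 bpm: 450/1.1856 = about 380 msec.
- 80 bpm: 450/1.1006 = about 409 msec.
- 50 bpm: 450/0.941 = about 478 msec, so nearly all of the true 450 to below 480 band would be reported as below 450.

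**Effect on change from baseline.** With a recorded baseline of 400 msec and an unchanged true value at 100 bpm, the fallback shows 474.3 - 400 = +74 msec, in the above-60 band.

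**Alternative reading.** If RR meant HR/60, dividing by RR^(1/6) would be right, but this contradicts the stated RR = 60/HR and would make the tier 2 formula wrong.

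**The case against.** The strongest argument concerns reach. The faulty formula is the last of three tiers. It applies only when QTcF and QT are both absent while QTcB and HR are present, and nothing in the documents shows that such a record exists. ECGs after screening are few (Day 1 and Weeks 4, 8, 12, 32 and 48). The QTcF output is descriptive: no test is planned on it and section 11.8.6 attaches no management rule to it. The formula is the same in every arm, so a distortion between arms would require the arms to differ in heart rate or in how often QT is missing. The derived table is also not the only view of the data, because all ECG data are to be listed and Protocol 9.3.2 has the investigator evaluate the readings. All of this stands. It limits the consequence, but it does not make the formula right.

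Two further objections are weak. The SAP does not define QTcB, so the check needs Bazett's square root; that is its ordinary meaning, and division would be right only if QTcB were QT/RR^(1/6), a weaker correction than Fridericia's. An operator misread from the PDF cannot be wholly excluded, but the neighbouring QT formula has the same layout and reads correctly.

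The worked records illustrate what can happen. They are not expected effects.

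**Conclusion.** The formula is wrong as written. When this branch is used, it returns QT/RR^(2/3) in place of Fridericia's QTcF at every heart rate except 60 bpm. The error is +18.6% at 100 bpm and -5.9% at 50 bpm, enough to move records across the absolute and change-from-baseline categories in either direction. This rests on one assumption, that QTcB means Bazett's correction. The number of affected records is unknown and may be zero, and no efficacy result is involved. It should be corrected, but it does not threaten the trial's conclusions.

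**What to change.** In SAP section 11.8.6, change the last fallback to QTcF = QTcB × RR^(1/6), keeping RR (seconds) = 60/HR, and state that QTcB = QT/RR^(1/2). Make the same change in the program. Count the records that use this branch; if there are any, rerun the QTcF summaries and the marked-abnormality tables. A quick program check is that the QT route and the QTcB route return the same QTcF on records that hold both QT and QTcB.

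The cost is one operator in the text and one in the code, plus the sign-off that SAP section 2.0 requires for a version updated after finalization. No new data are needed.
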